**I.    Hypotheses**

Multiple sclerosis (MS) is a progressive disabling disease of the central nervous system (CNS) which is associated with substantial personal, financial and societal costs. There now are 15 approved disease modifying therapies (DMTs) available, and data supports that early intervention is associated with best outcomes. The ultimate cause of MS remains unknown, but increased risk is associated with a host of genetic and environmental factors. First degree relatives (FDRs) of MS patients have a 10-20 fold increased risk of being diagnosed with MS themselves. But diagnosis, still, is delayed for many, in part due to lack of a specific biomarker of disease activity, and also due to vagueness of early symptoms in many. More recent studies, have clearly outlined a prodrome in individuals ultimately diagnosed with MS, prior to overt clinical symptoms typical of MS. Thus, it would be extremely helpful if we could develop a risk stratification algorithm that outlined those with both high and low risk of developing MS as early as possible in the disease process. The central hypothesis of this protocol is that it is possible, using FDRs of patients with MS and assessing a variety of both known and unknown risk factors for MS, to define a risk algorithm for earliest signs of development of MS. In addition, while starting with a relatively limited cross-sectional analysis, we hypothesize that development of a larger, longitudinal study will allow us to improve sensitivity by simple accrual of larger numbers of participants over time with the endpoint of early signs of MS on MRI scans, but also improve sensitivity by adding additional markers of MS risk as they become available.

**II.    Specific Aims**, among asymptomatic first degree relatives (FDRs), aged 18-30, of multiple sclerosis (MS) patients:

- 1: Determine the prevalence of brain MRI lesions disseminated in space (DIS), consistent with MS
- 2: Gather data on potential risk factors or early signs related to MS development, including markers for: genes, immunological function, environmental factors, neuroaxonal damage, Vitamin D levels, lipid metabolism, activity levels, mood abnormalities, and cognitive function. From this, develop a risk factor score, incorporating all relevant potential markers of increased risk of DIS.
- 3: To use this pilot, cross-sectional study as a base for development of a long-term, longitudinal, multi-center study to determine genetic and environmental risks for pre-symptomatic MS
- 4: To create and maintain a biobank of specimens for future analysis as other potential biomarkers become available.

**III.    Background and Significance**

MS is a progressive, inflammatory and degenerative condition of the CNS with mean clinical onset at age 30^1. MS is the most common CNS inflammatory disorder, with a prevalence of about 1/500 women and 1/1000 men in Colorado. It is a major cause of disability in young adults, and financial and psychosocial costs to the patient and society are great. Diagnosis remains challenging, as early symptoms may be vague and transient, and there is no highly sensitive and specific biomarker or diagnostic test. But there are now 15 disease modifying therapies (DMTs) available, all of which are most effective in those who are younger and relatively newly diagnosed. Delays in treatment are associated with greater accumulation of clinical symptoms and magnetic resonance imaging (MRI) scan abnormalities. Thus, there is a substantial need to develop early detection techniques for MS, so as to treat as early as possible.

But what is early? While clinical symptoms are the first overt indication of MS, evidence is rapidly expanding that there is a prodrome, or pre-clinical phase, prior to first symptoms and then diagnosis of MS. A clinical prodrome may be defined as the time between the onset of decline in a baseline level of functioning until formal diagnostic criteria are met. In the Nurses Health Studies I and II, the 341 women diagnosed with MS after entry into the study had lower levels of physical activity four to six years prior to MS diagnosis compared to age-matched control women. This prodromal period may be associated with

increased health care use and costs, as seen in a recent Canadian study of the five years preceding the diagnosis of MS. In an Argentinian case-control study, diminished cognitive performance in school was reported in individuals who developed a first attack consistent with MS, so-called clinically isolated syndrome (CIS), up to 10 years after leaving school. MRI scans also detect many asymptomatic lesions in MS, especially early in the course. Similarly, individuals destined to develop MS have early signs of anxiety and depression several years prior to diagnosis of MS. The majority of patients with CIS have already developed MRI evidence consistent with demyelination at some prior, indeterminate time point, i.e. the first scans typically show multiple areas of abnormality that have not been associated with any clinical symptoms. In CIS clinical trials, the average number of asymptomatic lesions on first brain MRI scan after a first clinical attack has exceeded 17. In addition, a small percentage of people undergo MRI scans for reasons seemingly unrelated to MS, yet the scans reveal abnormalities highly consistent with MS. This is referred to as radiologically isolated syndrome (RIS), and there is now a clinical trial underway to determine if very early treatment is beneficial in these patients (NCT02739542). Both CIS and RIS are predictive of new clinical disease activity consistent with MS. In a study of RIS, over a quarter of participants had cognitive impairment similar to that seen in MS. RIS, CIS and early onset RRMS are all associated with diminished brain volumes compared to age matched controls, suggesting neurodegeneration occurs very early, even in the prodromal phase.

Damage to the neuronal structures of the CNS can also be seen early in MS. Presumed damage to neural tissue has been associated with elevated levels of the neuronal cytoskeleton, Neurofilament light (NfL), in CIS and early MS patients, and are independently associated with relapses, disability progression, and MRI markers of brain lesion volume and atrophy. Similarly, evaluation of lipids may be important in early MS. MS is a demyelinating disorder of the CNS, and about 25% of total body cholesterol is located in the brain, most incorporated in the myelin sheaths wrapping around axons. Comorbidities linked to dyslipidemia are associated with increased risk for development of MS and disability progression. After CIS, elevated total cholesterol (TC) level has been associated with Gad-enhancing lesions, and TC and LDL levels have been associated with development of new and newly enlarging T2 lesions on brain MRI. Four years after CIS, and with use of interferon, there are rapid decreases in LDL, HDL, and TC, which then are followed by a slow return to baseline levels. Greater percent decrease in HDL at 3 months is associated with less brain atrophy over four years. Thus, abnormal lipid profiles appear to be associated with damage to the CNS, even early in the course of MS. Neither NfL nor lipid profiles have been evaluated as early markers CNS damage in pre-symptomatic individuals at high risk of developing MS.

The preponderance of evidence is consistent with the concept that MS results from the imposition of one or more environmental insults in individuals with a genetic background that predisposes them to MS. Epidemiological studies have identified both genetic (over 200 genes have been identified) and environmental risk factors (exposure to Epstein-Barr virus, obesity, vitamin D deficiency, and smoking) associated with the development of MS, and/or more progressive disease over time, but the triggers at onset remain unknown. Finally, asymptomatic individuals with parents or siblings with MS (first degree relatives - FDRs), have a 10-20 fold increased lifetime risk of developing MS compared to those without a relative with MS. This translates to about 4-5% of girls/women and 2-3% of boys/men who might be ultimately diagnosed with MS in their lifetimes. Diagnosis in multiple family members enhances this risk further. In addition, a variety of cross-sectional MRI studies have identified that about 10% of asymptomatic FDRs of MS patients have brain MRI lesions that could be demyelinating in nature, including fulfilling criteria for lesions disseminated in space (DIS). Thus, given that the median age of onset of relapsing MS is about 30 in multiple studies, we might expect that by age 30, 2-5% of FDR might have developed MS, but up to 5-10% may have developed MRI signs that place them at risk of developing MS, i.e. RIS.

In the recent Genes and Environment in Multiple Sclerosis (GEMS) study of 65 female FDRs of MS patients, those with a combined genetic (based on 64 known single nucleotide polymorphisms, SNPs, in 2012) and environmental (female sex, prior history of mononucleosis and smoking) high risk score were compared to FDRs with a lower score for developing MS. Those with a high risk score showed a trend toward higher BMI and weight, but there were no differences in age, height, cigarette smoking exposure,

25-hydroxyvitamin D level, or history of infectious mononucleosis or migraine. Five (four in high risk, one in low risk groups) of the 65 women had MRI evidence of lesions disseminated in space as seen in MS. Those in the high risk group had relatively impaired quantitative vibratory sensation testing, but there were no differences in quantitative brain volume measurements or retinal nerve fiber layer (RNFL) thickness on optical coherence tomography. The overall conclusion of this cross-sectional study was that high risk individuals showed early subclinical risk signs of MS, noting the study was underpowered to detect a difference in neuroimaging outcomes between higher-risk and lower-risk individuals.

Type I diabetes (T1D) shares many clinical and immunological features with MS, including that FDRs of T1D are at high risk of developing T1D. In our institution, the long-term Diabetes Autoimmunity Study in the Young (DAISY) has sought to understand specific risk factors associated with this T1D development. [name] and associates have identified loss of B cell anergy in some FDRs' of T1D patients. Also here at the University of Colorado, Anschutz Campus, our colleague, [name], and associates have identified a unique, pathogenic T cell population in T1D, an expansion of CD40 on CD4+ cells. Subsequently, we have shown a similar expansion of CD40 expression in MS patients of all ages compared to controls. Studies looking at CD40 expression in FDRs of T1D patients are underway. Thus, it is possible both of these immunological biomarkers, B cell anergy and T cell overexpression of CD40, may be present in FDRs of MS patients.

Innovation – The GEMS study described above is one approach to identification of early MS, but it had several limitations. It used a pre-defined risk score, including a SNP analysis of just 64 SNPs, when more recent analysis suggests over 200 may be relevant. It employed a long, detailed, and expensive brain MRI, but did not include spine or FLAIR\* analysis. The cost limited participation. GEMS did not include potential immunological markers, markers of CNS damage (such as NFL or lipids), activity levels, or a detailed environmental screen. Due to privacy issues, they were unable to verify the MS diagnosis in FDRs. Finally, it was limited to 100 patients, of which only 65 (females only) were analyzed. Other studies (as yet unpublished) designed to look at risk factor algorithms for development of MS are employing larger numbers of patients, but minimal, if any, MRI analyses, no or minimal immunological or CNS damage markers, and no activity levels. Most importantly, they are using full clinical diagnosis of MS as the outcome measure, greatly limiting the number of “positive” patients, and biasing toward a much later time in the disease process. Thus, our study has great innovative value for several reasons:

- a. We will define pre-symptomatic MS in 300 FDRs using stringent MRI criteria, including FLAIR\* sequences, thus significantly increasing sensitivity and detection in the prodromal phase. Proband MS patients will be defined from our own population of MS patients known to fulfill formal diagnostic criteria for MS.
- b. We will analyze genetic, immunological, vitamin, lipid, viral, and CNS damage markers; activity levels; and a mood and cognitive screen, with the goal of defining an expanded risk stratification scheme, not a pre-defined one
- c. We will include a detailed environmental screen, employing approaches very similar to the DAISY study, and [name], lead epidemiologist in DAISY, will participate as a Co-PI.
- d. We will compare those FDRs with and without brain MRI abnormalities to each other, and to non-FDR controls (blood and environmental screen, not MRI)
- e. We will create a biobank of blood, both plasma and PBMCs, including pre-processed serum/plasma and RNA, allowing us to add to the risk stratification model over time.

#### **IV. Preliminary Studies**

The background for the entire study is as listed above under Significance. We have extensive experience in blood and tissue banking, as [name] has been director of the Rocky Mountain MS Center Tissue Bank, which has collected over 500 autopsied brains and spinal cords for distribution to researchers in the US and abroad. [name] is head of our MS Center's Biobank of CSF and blood specimens. In addition, references 73-75 outline results with T1D and MS patients with potential immunological abnormalities relevant to FDRs of MS patients. Similarly the DAISY study references speak to the capacity to do detailed environmental screening in a very similar population of young patients and the expertise of [name]. Drs.

[name] and [name] have already developed the lab tests described. NfL (Quanterix) and lipid studies are commercially available and we have an agreement with Quanterix to perform the studies as in references 25-29. We also have performed over 50 clinical trials in MS, and have significant experience with large recruitments, including over 450 for our Biobank and several hundred for a study looking at development of a JC Virus serology test (the STRATIFY-1, and STRATIFY-2 studies), for which we were one of the largest recruiters internationally.

## **V. Research Methods**

Approach - The concept in this pilot study is to perform a cross-sectional analysis of the FDRs of MS patients. FDRs were explicitly chosen as they have enhanced risk of MS, thus enriching for abnormal, pre-symptomatic MRI scans. Broadly, we will perform an abbreviated, “screening”, brain MRI in 300 neurologically asymptomatic FDRs; draw blood for genetic, immunological, vitamin, lipid, viral, and CNS damage markers; and do an environmental screen, with mood and cognitive screening tests. Activity levels will be monitored with step analysis with the Godin Leisure-Time Exercise Questionnaire (GLTEQ), which has been validated in both adults and children with MS. FDRs with abnormal brain/spine MRIs fulfilling DIS will then be compared to age-and sex-matched FDRs *not* having MRIs fulfilling DIS, and to age-and sex-matched non-FDRs who do not carry a diagnosis of MS or have symptoms suggestive of MS (no MRI for the latter group, but all other measures taken). The long-term goal is to create a platform for a longitudinal study, likely at multiple sites, with the capacity to interrogate stored samples of DNA, RNA, plasma and PBMCs with associated environmental screening and the screening MRI scans as described above. As part of this, we also have had preliminary discussions regarding partnering with Savvysherpa for development of a long-term activity level monitoring system specifically for MS.

**A. Outcome Measure(s):** Individuals will be defined as having pre-symptomatic MS if they have brain/spine MRI abnormalities fulfilling DIS as defined by the Swanton criteria. Importantly, we will also obtain sequences which allow for determination of whole brain volume measures. The following MRI sequences will be obtained:

1. Whole brain T1-weighted images acquired using 3-Dimensional fast spoiled-gradient recalled acquisitions (T1-3D-FSPGR) with 1 mm slice thickness and isotropic voxel dimensions.
2. Whole brain 3-Dimensional Double Inversion Recovery (DIR) acquisition with 1.5 mm slice thickness.
3. Whole brain T2-weighted Fluid Attenuated Inversion Recovery (FLAIR) images with 1 mm slice thickness and isotropic voxel dimensions will be combined with
4. Whole brain T2\*-weighted segmented echo-planar imaging (segEPI) images with <=1 mm slice thickness and isotropic voxel dimensions to obtain FLAIR\* images.

The sequences were specifically chosen to: a) screen brain with the greatest specificity (FLAIR\*); b) allow for later volumetric analysis of the brain; and c) use the most sensitive technique for cortical and subcortical brain lesions (3D-DIR).

**B. Description of Population to be Enrolled:** The population will be a total of 300 women and men, of all races and ethnicities, between the ages of 18-30, inclusive, who have no symptoms of MS, but have at least one FDR with documented MS fulfilling McDonald 2017 criteria. Up to 1000 will be screened for inclusion, but some will be excluded due to inability to undergo a brain/spine MRI or have blood drawn, lack of interest after discussion of study requirements, or symptoms concerning for MS (the latter will be referred to a qualified neurologist for evaluation). FDRs with one or more siblings/parents with MS will be included, and more than one FDR of a proband MS patient will be allowed. A control group (based on # of FDRs with positive MRIs - we anticipate 15-30) of age- and sex-matched controls who have no known family members with MS (out to first cousins and grandparents) will have blood drawn and fill out the environmental questionnaire, but will not undergo a brain MRI. The controls will be matched 1:1:1 for those FDRs with positive MRI scans suggesting pre-symptomatic MS and those age-and sex-matched FDRs who do NOT have positive MRI scans suggesting pre-symptomatic MS. The ages were specifically chosen so as to have a good opportunity to collect an adequate number of MRI-positive, asymptomatic participants prior to the known median age of MS clinical onset (30 years), but not so young as to lower the likelihood of detecting asymptomatic brain MRI lesions.

1. FDR Inclusion Criteria
  - a. Male and female
  - b. All races and ethnicities
  - c. Ages 18-30
  - d. Must have a parent, sibling or child with MS fulfilling McDonald 2017 criteria
  - e. No symptoms suggestive of MS on formal screen
  - f. Ability to undergo a non-contrast MRI and venipuncture, and perform an environmental screen, mood screen and cognitive test
2. FDR Exclusion Criteria
  - a. Symptoms suggestive of MS on formal screen
  - b. Prior diagnosis of autoimmune disease that may be associated with CNS dysfunction and MRI lesions, e.g. Sjogren's
3. Non-FDR Inclusion Criteria
  - a. Male and female
  - b. All races and ethnicities
  - c. Ages 18-30
  - d. Must NOT have a FDR (parent, sibling, child) or second degree relative (grandparent, aunt or uncle) with MS fulfilling McDonald 2017 criteria
  - e. No symptoms suggestive of MS on formal screen
  - f. Ability to undergo venipuncture and perform an environmental screen.
4. Non-FDR Exclusion Criteria
  - a. Symptoms suggestive of MS on formal screen
  - b. Prior diagnosis of autoimmune disease that may be associated with CNS dysfunction and MRI lesions, e.g. Sjogren's

FDR participants will be enrolled from among the FDRs of MS patients seen at the Rocky Mountain Multiple Sclerosis Center at the University of Colorado in Aurora, Colorado (RRMSC at CU). Our center has approximately 3500 unique patients, of whom nearly all have asymptomatic FDRs, many in the appropriate age range. Documented MS proband patients will be made aware of the study via interactions in the office, our newsletter, and IRB-approved information given to them for their FDRs. FDRs who are then interested will initiate contact with the research group. If this does not provide adequate enrollment, we will recruit by local advertisement through known offices of neurologists in the Denver and surrounding regions. Age- and sex-matched non-FDR controls will be recruited from the friends of FDRs who are positive on the screening MRI, or will be recruited from local recruitment in the department of Neurology offices, from those non-MS conditions. FDRs and controls will be screened on the phone for basic demographic criteria (e.g. age, location where they live) and a checklist of basic MS symptoms, and to be certain they do not have previously undiagnosed MS or other autoimmune/neoplastic disorders. Those with concerns for MS at screening will be referred to a qualified neurologist for assessment.

### **C. Study Design and Research Methods:**

1. Prescreen FDRs by phone for ability to participate and lack of MS symptoms, using a standardized script to exclude those with overt MS symptoms. Proband MS patients will have documented MS by McDonald 2017 criteria.
2. Qualified FDRs will be scheduled for a study visit after completing a pre-screening questionnaire by phone. If they are not excluded by pre-screen, and wish to participate, a study visit will be scheduled. A waiver of documentation of consent will be obtained over the phone so as to instruct participants to fast from midnight prior to the first study visit. This will also allow them to fill out the environmental questionnaire on-line before their visit and at their convenience. The environmental survey must be completed at least three days prior to their visit. If not, the study visit will be canceled and rescheduled once its complete.
3. A study visit will include (See Table of activities below):
  - a. Read, ask questions regarding, and sign the consent.
  - b. Document completion of environmental questionnaire.
  - c. Obtain a measured height and weight, and compute a Body Mass Index (BMI)
  - d. Perform a non-contrast brain MRI (per section V.A)

- e. Perform a fasting Blood draw consisting of no more than 100 ccs of blood.
  - i. Blood drawn at the primary study visit will be a maximum of 100 ccs to be processed in the following fashion. Participants will not be made aware of their blood sample results
    - 1. 30 ccs for immediate cell sort by [name] into T and B lymphocytes, for CD40 expression studies, requiring primary analysis with fresh cells, and done on all samples. Also for HLA analysis.
    - 2. 20 ccs processed for delayed analysis of SNPs, viral serologies (Herpes Simplex Virus 1 and 2, Cytomegalovirus, Varicella-Zoster Virus, and Epstein-Barr Virus), vitamin D levels, and neuroaxonal (NfL - Quanterix) and myelin damage (lipids), which all can be performed on stored samples.
    - 3. 50 ccs processed and stored for delayed analysis of plasma and PBMCs, RNA and DNA, for studies not yet determined
- f. Perform the Perceived Stress Scale and the Neuro-QoL screen for anxiety and depression;
  - i. Participants screening for concerns for suicidality on the mood screen will be referred to an emergency room for evaluation.
- g. Perform a Symbol Digit Modality Test, a screen for cognitive function. The latter will be done in the written format.
  - i. Participants will not be advised of Cognitive screen results.
- h. As a measure of physical activity, we will use Godin Leisure-Time Exercise Questionnaire (GLTEQ), which measures mild, moderate and strenuous physical activity during a typical seven day period. This has been validated in MS, and is scored either into three levels of activity (sedentary, moderately active, or active), or may be used as a continuous measure.
- i. As a dietary assessment, we will use the Harvard 2007 Booklet FFQ, which is a semi-qualitative food frequency questionnaire used to assess intake of various nutrients over the past year. This has been robustly validated in a variety of populations, and nutrient intakes are computed by assigning a daily frequency weight.

4. MRIs will be read by a board-certified neuroradiologist ([name]) with extensive experience in reading brain MRIs in general, and MS MRIs in particular. All FDRs will receive a follow-up contact concerning the results of their MRI within one week. FDRs with a brain MRI fulfilling criteria for DIS will be referred to a qualified neurologist to determine if they should be treated or monitored more closely. Individuals with abnormal brain MRI scans not suggestive of or fulfilling DIS criteria, but having non-specific brain lesions (as can be seen with migraine and many other conditions), also will be referred to a qualified neurologist for evaluation as needed. Those FDRs with unexpected abnormalities (e.g. severe sinus disease, pineal cyst, pituitary abnormality, cavernous angioma, etc.) will be referred as necessary to a qualified physician.

5. FDRs with a positive brain MRI showing lesions DIS will be asked to return within four months for a repeat blood draw of no greater than 100 cc of blood, to be compared to age-and sex-matched FDRs without a positive brain MRI (who will also be asked to return within 4 months for the repeat blood draw) and age-and sex-matched non-FDRs, both in a 1:1 ratio. The former will be identified from those already in the study, and the latter will be recruited from age- and sex-matched friends of the FDRs with positive brain MRIs. The non-FDRs will be prescreened and perform all the study procedures as the FDRs on the first study visit, with the exception of the MRI.

- a. This blood draw will be for B cell anergy and cytokine studies in [name] lab, and repeat CD40 studies on non-FDR controls (i.e. not already done by [name] lab) which require fresh cells, but done only on this subset of participants. The rest of the blood will be processed and stored as described in C3ei.3 above for potential future use.

6. Data will be stored in a HIPAA-compliant database. Analysis will be done via case-cohort approach with the roughly 15-30 MRI-positive participants, controls as noted, and looking at the markers individually and together.

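### A DIS-positive relative whom the referral neurologist finds to have had earlier MS symptoms would still be analysed as a pre-symptomatic case, because that finding is never returned to the study

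*Combined protocol and SAP*

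**What the plan says.** **Population.** Section II sets the aims "among asymptomatic first degree relatives (FDRs), aged 18-30, of multiple sclerosis (MS) patients". The inclusion criteria in V.B require "No symptoms suggestive of MS on formal screen".

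**How symptoms are checked.** The formal screen is not described as anything beyond a telephone contact. V.C item 1 describes "using a standardized script to exclude those with overt MS symptoms". The recruitment text that follows the criteria in V.B adds "a checklist of basic MS symptoms, and to be certain they do not have previously undiagnosed MS or other autoimmune/neoplastic disorders", and people who raise concern at screening are referred to a neurologist. The Visit 1 list in V.C item 3 and the Study Procedures table contain no neurological examination and no symptom history. The SDMT and Neuro-QoL are collected, but are not used to establish asymptomatic status.

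**Case label.** V.A: "Individuals will be defined as having pre-symptomatic MS if they have brain/spine MRI abnormalities fulfilling DIS as defined by the Swanton" criteria. Only the scan enters this rule.

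**After a positive scan.** V.C item 4: "FDRs with a brain MRI fulfilling criteria for DIS will be referred to a qualified neurologist to determine if they should be treated" or watched more closely. No section says that the neurologist's conclusion is obtained, recorded or used. V.C item 6 takes the roughly 15-30 MRI-positive participants into the analysis.

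**The concern.** The label makes two claims: that the scan shows dissemination in space, and that the person has had no MS symptoms. The study checks the first on the scan and the second by telephone self-report.

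The thresholds for the second also differ. The script in V.C item 1 is aimed at overt symptoms, while the criterion in V.B excludes symptoms merely suggestive of MS. Section III itself says "Diagnosis remains challenging, as early symptoms may be vague and transient", and that is the kind of symptom that would pass one threshold and fail the other.

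For a relative who raised no concern on the phone, the referral after a positive scan is the first clinical assessment in the plan. It falls on exactly the people who become cases, and it can show that someone never met the eligibility criterion or that another condition explains the lesions. Section III says that NfL is raised in CIS and early MS, and V.F names NfL as a candidate for the risk score. A few symptomatic cases could therefore make NfL look like a pre-symptomatic marker when it is marking disease already under way.

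**Working it through.** **1. The plan's case count (V.F item a).** 0.05 × 300 = 15 and 0.10 × 300 = 30, as stated.

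**2. Weight of one case.** 1/30 = 3.3% and 1/15 = 6.7% of the case group.

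**3. Symptomatic cases with raised NfL.** The documents give no rate of symptomatic cases and no size for the NfL difference. Assumed: 10-20% of cases are symptomatic, their mean NfL is 1-1.5 SD higher, and NfL is otherwise unrelated to case status. The plan names no test for NfL, so a two-sided 5% t-test of cases against one equal control group is also assumed.

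With k of n cases shifted by d, the mean difference is (k/n) × d. The SD in the case group rises to about √(1 + (k/n)(1 − k/n)d²). For 6 of 30 at d = 1.5 this gives a difference of 0.30 and an SD of √(1 + 0.2 × 0.8 × 2.25) = 1.17. The wider spread has to be allowed for, so rejection rates were simulated (200,000 data sets per row):

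| n per group | symptomatic cases | d = 1 | d = 1.5 |
|---|---|---|---|
| 30 | 0 | 5% | 5% |
| 30 | 3 (10%) | 6.1% | 7.3% |
| 30 | 6 (20%) | 10.4% | 16.0% |
| 15 | 2 (13%) | 5.8% | 6.5% |
| 15 | 3 (20%) | 7.0% | 9.2% |

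The range is about 6-16% at 30 v 30 and about 6-9% at 15 v 15. If the number of symptomatic cases varies at random around 10-20%, the upper ends become about 18% and 11%.

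**4. Cases with another cause and control-level markers.** These act in the opposite direction. Take the plan's HLA odds ratio of 2.9 with 30 cases and 60 controls, and assume a control frequency of 0.30 (not given in the plan), a two-sided 5% level and no matching. Power is then 0.65, close to the stated 64%.

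- Exposure in true cases: 2.9 × 0.30 / (1 + 1.9 × 0.30) = 0.554.
- With 20% of cases at control level: 0.8 × 0.554 + 0.2 × 0.30 = 0.503.
- Observed odds ratio: (0.503/0.497) / (0.30/0.70) = 2.36. Power falls to 0.47.
- With those cases and their controls removed (24 v 48), the odds ratio returns to 2.9 and power is 0.55.

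**The case against.** **The screen is more than a script for overt symptoms.** This is right. V.B adds a checklist, an intention to rule out undiagnosed MS and other autoimmune or neoplastic disorders, and neurologist referral where concern arises. A prior diagnosis of a relevant autoimmune disease also excludes. The script itself is not in the documents, so its real threshold is unknown. It remains true that all of this is self-report or history, and that a person who reports nothing is not examined before being labelled.

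**Retention of symptomatic cases is inferred.** This is also right. A reader might infer that the plan forbids reclassification. It does not; it is silent. But a scan-only definition with no return of the neurologist's finding leaves no route by which a case could be relabelled.

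**Imaging was chosen deliberately over clinical diagnosis.** It was, and Section III gives the reason. A reader might go on to infer that the Aim 1 prevalence is inflated. The documents do not support that: Aim 1 is the prevalence of DIS lesions on MRI, and that count stands whatever the neurologist finds.

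**The other-cause part is really about MRI specificity.** Largely so. The part about eligibility is the symptomatic one, since no imaging sequence can show whether someone previously had symptoms.

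**Checking only the cases is one-sided.** This stands. MRI-negative relatives are not routinely referred and non-FDR controls have no scan, so removing cases on the neurologist's word has no counterpart among controls. That rules it out as the main analysis.

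**The study calls itself an underpowered proof of concept.** True, but its results are meant to ground a larger longitudinal study, so what the case group represents still matters.

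**Conclusion.** The concern holds as a gap in how Aim 2 cases are labelled. No stated figure in the plan is wrong because of it. On the plan as written, a DIS-positive relative found to have had MS symptoms before Visit 1 remains a pre-symptomatic case, and the one planned assessment that could show this is not used.

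The weight of a single case follows from the plan's own numbers. The false-positive ranges do not: they rest on an assumed share of symptomatic cases, an assumed NfL difference and an assumed test, and they show what could happen rather than what is expected. A reader might infer that Aim 2 will be biased towards positive findings. The documents do not support a single direction, because cases with another cause and control-level markers would weaken associations. The point is worth acting on because the case group is small and the information will be generated anyway.

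**What to change.** - **V.C item 4:** record, with consent, the neurologist's conclusion for each DIS-positive relative: MS symptoms or signs dating from before Visit 1 (yes/no), and an alternative cause for the lesions (yes/no).
- **V.A and V.F:** keep every DIS-positive scan in the Aim 1 prevalence and in the main Aim 2 analysis. Report how many were found symptomatic or otherwise explained, and how many reports were not returned. Reserve the label of pre-symptomatic MS for the remainder.
- **V.F item c:** repeat the Aim 2 contrasts without the symptomatic or otherwise explained cases, dropping their matched controls with them, as a sensitivity analysis. State that controls have no equivalent check, so the exclusion is one-sided.
- **V.B and V.C item 1:** reconcile the overt threshold in the script with the suggestive threshold in the criterion.

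The cost is one short form or clinic letter for each of the 15-30 people already being referred, a line in the consent form and one added analysis. Some reports may not come back. The referral pathway itself does not change.
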